After each cohort, a review of safety data (eg, AE [including potential psychotic symptoms and behavior], vital signs, laboratory data, standard 12-lead ECG, etc.) and lurasidone injectable suspension exposure data for all subjects (or at least 5 lurasidone and 1 placebo subjects completed) in each cohort will be performed. Subsequent dosing at the next dose level/cohort will not occur until safety and exposure data (from at least 14 days after the single lurasidone injectable suspension dose) have been evaluated by the Safety Review Team (SRT). The SRT consists of the PI, the Sponsor's Responsible Physician or designee, the Sponsor's Project Medical Lead, the Sponsor's Head of Translational Medicine and Early Development team or designee and the Medical Monitor. The SRT will also determine if sentinel subject dosing is required for study cohorts after Cohort 1.

The decision to proceed to the next dose level/cohort and at what dose level will also be made by the voting members of the SRT, based on a review of the clinical observations, laboratory data, and exposure data, and will require a majority agreement concerning acceptable safety and tolerability of lurasidone injectable suspension. Based on these safety reviews, a more conservative dose escalation may be used that will be less than the planned dose escalation, or subsequent cohorts may repeat a dose level or de-escalate. For each cohort, the SRT will monitor and review AE and exposure data 14 days and 28 days after the injection dose.

Treatment assignments for a particular cohort may be unblinded during a safety review meeting, but only after a blinded review of the safety data has been completed. PK exposure data will be utilized in the safety review; thus, it will be necessary for the bioanalytical laboratory to be unblinded to treatment assignment for the subjects.

Determination of the Minimum Intolerable Dose (MID) and Maximum Tolerated Dose (MTD)

The MID will be defined as the dose of Lurasidone injectable suspension at which dose limiting toxicity (DLT) occurs. Dose-limiting toxicity is indicated by the occurrence of intolerable AEs, which are not fully defined a priori, but will be determined from the study data at the SRT meetings. Adverse events, including SAEs, which start prior to the study drug injection, will not be considered for stopping criteria.

Dose stopping criteria are provided in Section 9.3.

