^e Subjects will restart prior medications (including antipsychotics) on Day 29 under observation of clinical site staff.

Eligible subjects will be washed out/tapered off of their current antipsychotic medications over 5 to 6 half-lives prior to Day -8 (may begin Day -19). Subjects will be monitored for safety during tapering/washout. Subjects will be admitted to the clinical site on Day -12 and are required to be inpatient until Day 15.

Subjects will receive oral lurasidone 80 mg tablets on Day -7 and Day -6 (one dose per day), and be monitored for 5 days to ensure the subject is able to tolerate lurasidone (ie, absence of moderate adverse events). Subjects who tolerate dosing with oral lurasidone 80 mg will be eligible for randomization to receive a single lurasidone injectable suspension or placebo injection on Day 1.

Subjects who are discharged after Day 15 will check into the clinical site again on Days 22 and 29 for scheduled assessments. Subjects will follow protocol procedures to remain in-clinic through Day 33 as they restart their prior medications (including antipsychotics), under observation of the Investigator/clinical site staff (ie, restabilization period).

Subjects who remained in-clinic through Day 29 will remain inpatient through Day 33 as they restart their prior medications (including antipsychotics) under observation of the Investigator/clinical site staff (ie, restabilization period).

The restabilization period may be longer and subjects may remain in-clinic, as deemed necessary by the Investigator.

Subjects who discontinue the study prior to Day 29 will undergo assessments scheduled for Day 29 at the time of discontinuation (see Table 2). Subjects who discontinue the study after Day 29 but prior to Day 61 will undergo assessments scheduled for Day 61 at the time of discontinuation (see Table 2).

Subjects who complete the study per protocol will return to the clinic for a follow-up safety assessment on Day 61 (\pm 2).

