9.2. Dose Escalation/Safety Cohort Review

After each cohort, a review of safety data (eg, AE [including potential psychotic symptoms and behavior], vital signs, laboratory data, standard 12-lead ECG, etc.) and lurasidone injectable suspension exposure data for all subjects (or at least 5 lurasidone and 1 placebo subjects completed) in each cohort will be performed. Subsequent dosing at the next dose level/cohort will not occur until safety and exposure data (from at least 14 days after the single lurasidone injectable suspension dose) have been evaluated by the Safety Review Team (SRT). The SRT consists of the PI, the Sponsor's Responsible Physician or designee, the Sponsor's Project Medical Lead, the Sponsor's Head of Translational Medicine and Early Development team or designee and the Medical Monitor. The SRT will also determine if sentinel subject dosing is required for study cohorts after Cohort 1.

The decision to proceed to the next dose level/cohort and at what dose level will also be made by the voting members of the SRT, based on a review of the clinical observations, laboratory data, and exposure data, and will require a majority agreement concerning acceptable safety and tolerability of lurasidone injectable suspension. Based on these safety reviews, a more conservative dose escalation may be used that will be less than the planned dose escalation, or subsequent cohorts may repeat a dose level or de-escalate. For each cohort, the SRT will monitor and review AE and exposure data 14 days and 28 days after the injection dose.

Treatment assignments for a particular cohort may be unblinded during a safety review meeting, but only after a blinded review of the safety data has been completed. PK exposure data will be utilized in the safety review; thus, it will be necessary for the bioanalytical laboratory to be unblinded to treatment assignment for the subjects.

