9.3. Determination of the MID and MTD

The MID will be defined as the dose of Lurasidone injectable suspension at which dose limiting toxicity (DLT) occurs. Dose-limiting toxicity is indicated by the occurrence of intolerable AEs, which are not fully defined a priori, but will be determined from the study data at the SRT meetings. The following criteria will be used as a guide:

- If 50% or more of the subjects receiving study drug have either multiple moderate AEs and/or a severe AE possibly related to study drug as determined by the SRT MID may have been reached, and safety data will be unblinded.
- If more than one subject but less than 50% of the subjects receiving study drug have either multiple moderate AEs and/or a severe AE possibly related to study drug as determined by the SRT a dose level/cohort may be repeated or a modified escalation may be employed, and safety data of the subject(s) in question will be unblinded.

The SRT may decide to stop dose escalation, repeat a dose, or de-escalate if the number, severity, or type of AEs indicates that higher doses would not be tolerated. In addition, the following stopping criteria for dose-escalation will also be used to assess whether to proceed to a higher dose level in the next cohort. Dose escalation will not occur, although a dose cohort may be repeated or de-escalate if any of the following criteria are met:

• Adverse Events

A SAE associated with the use of the study drug with a reasonable possibility that
the event may have been caused by the study drug occurs in any subject on
active drug.

• Cardiac Parameters

A confirmed value of QTcF interval > 500 ms or > 60 ms change from baseline,
 based on cardiologist over read ECGs occurs in any 2 subjects on active drug.

• Hepatic Parameters

- Liver function tests (alanine aminotransferase [ALT], aspartate aminotransferase [AST], or total bilirubin [TBL]) > 3 x upper limit of normal (ULN) occurs in any 3 subjects on active drug.
- Any one of Hy's law criteria are met for any subject on active drug.
- ALT or AST $> 8 \times ULN$.
- ALT or AST > 5 x ULN for more than 2 weeks.
- ALT or AST > 3 x ULN and (TBL > 2 x ULN or international normalized ratio [INR] > 1.5).
- ALT or AST > 3 x ULN with the appearance of fatigue, nausea, vomiting, right upper quadrant pain or tenderness, fever, rash, and/or eosinophilia (> 5%).

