• Injection site reactions will be assessed for severity according to each of the following categories (per the Investigator's judgement):

Local Reaction to Injectable Product	Mild (Grade 1)	Moderate (Grade 2)	Severe (Grade 3)	Potentially Life Threatening (Grade 4)
Pain	Does not interfere with activity	Repeated use of non-narcotic pain reliever > 24 hours or interferes with activity	Any use of narcotic pain reliever or prevents daily activity	Emergency room (ER) visit or hospitalization
Tenderness	Mild discomfort to touch	Discomfort with movement	Significant discomfort at rest	ER visit or hospitalization
Erythema/Redness	2.5 – 5 cm	5.1 – 10 cm	> 10 cm	Necrosis or exfoliative dermatitis
Induration/Swelling	2.5 – 5 cm and does not interfere with activity	5.1 – 10 cm or interferes with activity	> 10 cm or prevents daily activity	Necrosis

Reference: FDA Guidance for Industry "Toxicity Grading Scale for Healthy Adult and Adolescent Volunteers Enrolled in Preventive Vaccine Clinical Trials," 2007.

Adverse events, including SAEs, which start prior to study drug injection, will not be considered for stopping criteria.

Once a safety stopping criterion is reached, the study will not escalate beyond that dose level. If none of the stopping criterion has been attained, the study will proceed to the next higher dose level. Dosing of an additional cohort or cohorts at a dose between the identified MID and the highest dose below the MID may be conducted. The highest tolerated dose below the MID will be defined as the MTD for a single lurasidone injectable suspension dose.

If the MTD is not established, additional dose cohorts may be commenced until the MTD is reached.

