10.2.1. Pretreatment Events and Adverse Events

Pretreatment events will be recorded from the time informed consent is provided at screening until the time of first lurasidone oral tablet dose administration at Day -7.

Adverse events will be collected for each subject from immediately after the first lurasidone oral tablet dose administration at Day -7 until the follow-up visit at Day 61 (\pm 2).

Subjects should be queried in a non-leading manner, without specific prompting (eg, "Has there been any change in your health status since your last visit?"). See Section 11, Safety Reporting.

AEs and SAEs will be monitored throughout the study at all visits.

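### Section 9.3 excludes pre-injection events from the stopping criteria by start date alone, so a run-in event that becomes a related SAE after injection can miss the only binding adverse-event stop

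*Protocol*

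**What the plan says.** **Exclusion.** Protocol 9.3 says "Adverse events, including SAEs, which start prior to study drug injection, will not be considered for stopping criteria". The synopsis says the same: "Adverse events, including SAEs, which start prior to the study drug injection, will not be considered for stopping criteria". Neither place has a clause for worsening.

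**Binding rule.** In 9.3, "Dose escalation will not occur, although a dose cohort may be repeated or de-escalate if any of the following criteria are met". The adverse-event item on that list begins "A SAE associated with the use of the study drug with a reasonable possibility that" the drug caused it, and one subject on active drug is enough.

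**Discretion.** Alongside the binding list, "The SRT may decide to stop dose escalation, repeat a dose, or de-escalate if the number, severity, or type of AEs indicates" a tolerability problem above the current dose. Under 9.2, moving to the next dose "will require a majority agreement concerning acceptable safety and tolerability of lurasidone injectable suspension".

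**Run-in.** Subjects take oral lurasidone 80 mg on Days -7 and -6 and are then "monitored for 5 days to ensure the subject is able to tolerate lurasidone (ie, absence of moderate adverse events" (Protocol 6.1). Under 10.2.1, "Adverse events will be collected for each subject from immediately after the first lurasidone oral tablet dose administration at Day -7". An adverse event can therefore start before injection and still be present on Day 1.

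**Recording of worsening.**
- Protocol 11.1.1 allows an exacerbation of an existing condition to be an adverse event.
- Section 10.2.3 requires worsened examination findings after dosing to be recorded as adverse events.
- Section 11.1.2 asks for the same where a hospitalization or procedure was scheduled before consent and the condition worsens.
- Section 11.3 does not say whether an ongoing adverse event that worsens gets a new record or a new onset date.

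**SAP.** Section 18.1 moves an oral-period event into the injection period if its severity worsens, and leaves it in the oral period if severity is unchanged. The known-start rows of Appendix 2 assign events by start date only.

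**The concern.** This is the first human study of the injection (Protocol 6.3.1), and the run-in gives subjects the same active moiety by mouth. A mild reaction to the tablets that becomes serious after the depot injection is a signal the study should detect, and it cannot be reversed by stopping a daily dose. The exclusion looks only at when the event began, so it treats that case like an unchanged run-in symptom.

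What is lost is the mandatory character of the stop. The guide for the minimum intolerable dose in 9.3 is worded as a guide, and its lower tier needs more than one subject. The injection-site item gives a grading scale but no threshold. The QTcF and hepatic triggers rest on measured values. If the single related SAE is set aside, no adverse-event rule in 9.3 forces a halt.

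The SAP raises a related question of attribution: two of its rules put the same worsened event in different periods, and so in different table columns.

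**Working it through.** The plan gives no figure on this point, so the check is mainly a reading of the texts against one case, followed by simple arithmetic.

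**Test case.** An active subject has a mild adverse event with onset on Day -5. It continues past injection, and on Day 4 it worsens and becomes an SAE that may reasonably have been caused by the study drug.

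| Rule | Worsening kept on the same record | Worsening logged as a new event, onset Day 4 |
|---|---|---|
| Protocol 9.3, related-SAE stop | Not counted: start precedes injection | Counted: escalation barred |
| SAP 18.1, severity rating rises | Injection period | Injection period |
| SAP 18.1, serious but severity rating unchanged | Oral period | Injection period |
| SAP Appendix 2, known start date | Oral period; not an event of the injection period | Injection period |

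The result depends on a recording choice that the protocol does not settle. The SAP 18.1 rule itself describes one event that began in the oral period, continued and got worse. That is the same-record case. (Section 11.3 gives Day 1 as the start of adverse-event recording, but 10.2.1, Table 2 and SAP 18.1 all use the first oral dose on Day -7, which is followed here.)

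**Exposed window.** From the first oral dose on Day -7 to injection on Day 1, with no Day 0 under SAP 7.1: 7 days. Moderate events bar randomization, so events carried over are normally mild. Earlier washout events are pretreatment events, and an exacerbation after injection can be read as a new adverse event under 11.1.1.

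**Effect on the stop.** The threshold is 1 active subject. Excluding that subject gives 1 - 1 = 0, so the criterion is not met and the decision goes to the Safety Review Team. A majority of n voters is floor(n/2) + 1. Five roles are listed, but the voting members are not identified, so n is an assumption:
- n = 5: 3 votes, so escalation can proceed with 2 against
- n = 4: 3 votes
- n = 3: 2 votes

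**Effect on the tables.** One misplaced subject changes a dose column by 1/6 = 16.7 percentage points, for example 0/6 instead of 1/6 in the SAE table. Pooled placebo has up to 5 × 2 = 10 subjects, so there the change is 1/10 = 10.0 points.

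**Illustration only.** Let p be the true related-SAE rate per active subject, and s the share of those SAEs that began in the run-in and are excluded. The documents give neither. The chance that the binding stop fires among 6 active subjects is 1 - (1 - p(1 - s))^6:

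| p | s = 0 (all counted) | s = 0.10 | s = 0.25 | s = 0.50 |
|---|---|---|---|---|
| 0.05 | 26.5% | 24.1% | 20.5% | 14.1% |
| 0.10 | 46.9% | 43.2% | 37.4% | 26.5% |
| 0.20 | 73.8% | 69.6% | 62.3% | 46.9% |

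The larger values of s have no support in the documents. The table shows only how the one-subject rule responds.

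**The case against.** The strongest reply is that the literal reading is not the natural one. A mild run-in symptom is not an SAE until it meets a seriousness criterion, and here that happens after injection. Section 11.1.1 lets an exacerbation count as an adverse event, and whether it gets a new record is usually settled in CRF instructions, which are not among the documents. Other safeguards apply: SAEs go to the sponsor at once with the form due within 24 hours (11.4.1), the Safety Review Team reviews adverse events at 14 and 28 days, and the investigator may halt part or all of the study after consulting the sponsor (Section 13). The SAE stop already turns on a causality judgement. Excluding by onset is also a defensible way to keep effects of antipsychotic withdrawal and oral drug out of the rule. On the SAP side, 18.1 is the specific rule and could be taken to govern over an appendix on partial dates. Those tables come after database lock and do not affect escalation. An event that becomes serious would seldom still be rated mild.

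Much of this stands as a limit on impact. The class is small, the team can still stop, misplaced events remain in the listings, and the unchanged-severity branch will rarely be used. None of it repairs the text. The exclusion expressly names SAEs and refers to when they start. Section 11.1.1 permits a new record but does not require one, and the two passages that ask for one cover only examination findings and previously scheduled hospitalizations or procedures. Causality judgement decides whether an event qualifies, whereas the exclusion removes it before that question is asked. Appendix 2 also covers fully known dates, so a programmer faces two conflicting instructions.

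**Conclusion.** The concern holds. For an adverse event that starts between the first oral dose and injection and later becomes a related SAE in an active subject, the literal text of 9.3 turns a mandatory halt into a majority decision, unless the site records the worsening as a new event. The number of votes needed depends on who votes, which the protocol does not say. Whether the exclusion also reaches the guide for the minimum intolerable dose is unclear; the QTcF and hepatic triggers are unaffected.

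The SAP conflict is confirmed for known start dates with worsened severity. It misplaces events in summary tables without losing them.

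No frequency can be given, because the documents have no rate for worsening run-in events. The case for change rests on the importance of a one-subject stop in a first-in-human study and the low cost of closing the gap. Confidence is medium, since CRF instructions not seen here might already require a new record.

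**What to change.** 1. **Protocol 9.3 and synopsis.** Add: an event with onset before injection that increases in severity or becomes serious after injection counts toward the stopping criteria from the date of worsening, subject to the existing relatedness test. Events that do not worsen stay excluded.
2. **Recording.** Instruct sites, for example in 11.3, to enter such a worsening as a new adverse event dated at the worsening.
3. **SAP 18.1.** Extend the worsening rule to events that become serious, whatever the severity rating.
4. **SAP Appendix 2.** Add a matching branch to the known-start rows of the injection-period algorithm.

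The cost is one sentence by amendment in two places, one recording instruction, one phrase in 18.1 and one branch in Appendix 2. The downside is an extra record per worsened event and possibly an occasional halt from an event confounded by washout. The relatedness test limits that, and 9.3 still allows the dose to be repeated or lowered.

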9.4. Treatment Compliance

This is a single-dose study. Study drug will be administered at the clinical site. The date and time of study drug administration will be recorded.

9.5. Prior and Concomitant Medications

The following information on all concomitant medication administered will be recorded on the CRF and will include medication name, dose, dose unit, frequency, route, start date, stop date, and indication. Any medication or non-pharmacological therapy that is taken by or administered to the subject at any point during the course of this study must be recorded in the eCRF.

Information on the format and version of coding dictionary is provided in the Data Management Plan. All medications will be coded using WHO-DD.

9.5.1. Prior Medications

All prior antidepressants and mood stabilizers (eg, lithium, divalproex/valproic acid, carbamazepine) must be discontinued as tolerated and clinically appropriate starting on Day -12. All other psychotropic medication (except as described in Section 9.5.3), including antipsychotic medication, must be discontinued as tolerated and clinically appropriate starting on Day -12 in a manner that is consistent with labeling recommendations and conventional medical practice.

These prior medications will not be allowed until subjects have completed Day 30.

Initiation of new psychotherapeutic interventions (eg, a new course of psychotherapy) will not be permitted during the study through the restabilization period. Subjects who have participated in ongoing psychotherapy treatment for at least 12 weeks prior to screening will be permitted to continue this treatment during the study.

Additional medication use as specified in the exclusion criteria is prohibited prior to the study.

9.5.2. Concomitant Nonpsychotropic Medications

Non-psychotropic medications used to treat mild, chronic medical conditions may be used during Screening and after assignment of a subject number, if the dose and regimen have been stable (\pm 25%) for at least 30 days prior to Screening. The concomitant medication dose may change as needed (or be discontinued) after a subject number is assigned. In addition, use of nonprescription pain medications are allowed during all phases of the study provided these medications do not have a propensity for psychotropic effects and do not interfere with the evaluation of study medication. Medications for short-term treatment of a medical condition (no more than 10 days) are allowed with consultation with the Medical Monitor provided that the medications are not drugs that prolong the QT/QTc interval or CYP3A4 inhibitors or inducers (see Section 22, Appendix IV and Section 23, Appendix V, respectively).

9.5.3. Concomitant Psychotropic Medications

During the wash-out, treatment and post-treatment periods, treatment with benztropine (up to 6 mg/day) will be permitted as rescue medication and as treatment for movement disorders. In cases where benztropine is not available or a subject has had an inadequate response or intolerability to benztropine treatment, the following medications may be used to treat acute EPS: biperiden (up to 16 mg/day) or trihexyphenidyl (up to 15 mg/day) or diphenhydramine (up to 100 mg/day). Treatment with amantadine (up to 300 mg/day) will be permitted as needed for akathisia. Medications used to treat movement disorders should not be given prophylactically. Medications used for movement disorders should be tapered and discontinued prior to a subject number is assigned but may be reinstituted if symptoms emerge.

In situations where anticholinergic agents or any other agents that may cause sedation are administered, these should be taken at the same time each day and should not be taken within 12 hours of scheduled assessments. When the specified drugs are not available, similar drugs at equivalent dosages will be substituted in consultation with the Medical Monitor. Concomitant use of lorazepam, temazepam, or zolpidem is permitted with the following restrictions: lorazepam is permitted for clinically significant anxiety/agitation or as a sedative/hypnotic up to a maximum daily dose of 6 mg/day. Intramuscular lorazepam is permitted up to 4 mg/day for acute anxiety/agitation, as clinically indicated. Lorazepam should be used sparingly, when

clinically required, per Investigator judgment. Zolpidem (\leq 10 mg in any 24-hour period) and temazepam (\leq 30 mg in any 24-hour period) may be administered, as needed, as sedatives/hypnotics. Hypnotic agents should be administered no more than once nightly and should not be used in combination.

Medications used for the as-needed treatment of anxiety/agitation and insomnia (eg, lorazepam and zolpidem) should not be used in close temporal proximity (defined as administration within 2 hours of each other). When lorazepam or zolpidem or other specified medications are not available, another similar agent at equivalent doses will be permitted as specified by the Medical Monitor. Opiates may be allowed in rare cases for a limited period of time with prior authorization from the Medical Monitor. Subjects who require treatment with one or more of the medications listed in Section 22, Appendix IV or Section 23, Appendix V should be excluded or discontinued (as appropriate) from the study. Since these lists of drugs are not comprehensive, Investigators should use medical judgment when a subject presents with a medication not on the list or consult with the Medical Monitor for clarification.

